Study Visit 1 (primary care office): Once consented and randomized, the CHW will collect baseline data (study questionnaires, weight, height, spirometry), administer a caregiver needs assessment and assist caregiver in choosing 2-3 care coordination goals such as keeping appointments, reduce secondhand smoke exposure or using medications correctly. The CHW will conduct in-office asthma teaching (medications/devices/asthma care plan), coordinate specialist visits and assist caregivers in voicing questions/concerns about medications or treatment plans to the primary care provider. They will personally schedule patients for follow-up visits with the primary care provider. Home Visits 1, 2 and 3: The first three home visits will occur within 2, 4 and 6 weeks after enrollment. At the first visit the CHW will conduct an environmental assessment of the living area and bedroom for common asthma triggers. Based on those findings the CHW will educate regarding asthma trigger avoidance and give supplies to reduce those triggers (mattress and pillow covers, roach bait, mice traps, tiles for carpeted floors) at the second visit. The CHW will also review medications available for the child at home and whether forms/prescriptions have been completed for school. They will coordinate with the primary care team as needed. Video conferencing through a HIPAA-compliant application licensed by CHOP, including but not limited to Vidyo telehealth visits in MyCHOP, may be used for home visits that cannot be conducted in person due to health or safety concerns. For telehealth home visits, supplies will be provided to families via U.S. postal mail with caregivers providing confirmation of receipt. Study Visits 2, 3, and 4 (primary care) will occur at 3, 6, and 9 months post-randomization. At these visits, the participants will receive asthma maintenance care by the provider/clinician and pulmonary function testing (spirometry) in addition to the education and care coordination activities by the CHW as described in the first visit. A member of the research team other than the assigned CHW (Home Visitor) will administer study questionnaires at these visits. At Home Visit 4 at 12 months post-randomization the CHW will conduct an environmental assessment to document trigger reduction techniques in the home and review medications. At Study Visit 5 at 12 months post-randomization, the asthma control questionnaire (ACQ), additional study questionnaires, pulmonary function testing (spirometry) and care coordination goals will be completed. Study staff will administer a CHW satisfaction survey via telephone between 13 and 24 months post-randomization once all primary care and school interventions have been completed.

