### 6.3.2 Efficacy Analysis

The primary analysis will be based on an intention to treat approach and will include all subjects randomized at Study Visit 1. The primary efficacy endpoint will be the change in asthma control between Study Visit 1 and Study Visit 5. Secondary efficacy endpoints will include the change in asthma symptom days and school absences between Study Visit 1 and Study Visit 5.

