3.2 Randomization of children within Schools

Randomization at the child level proceeded using randomly permuted blocks with vary block sizes, as implemented using the Stata program "ralloc" (Ryan 2000). This program used randomly permuted blocks with block sizes of 2 and 4. Randomization was stratified by school and by clinic within school. There were two waves of randomization. The first occurred with the first recruitment of schools and the second with the second wave of schools.

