5.1.2 Measuring outcomes over time - irregular measurement times

Longitudinal model

Although the protocol calls for regular measurement times (Juniper's **Asthma Control Questionnaire** is a validated survey and will be administered by the CHW at baseline, 3 months, 6 months, 9 months and 12 months), in all likelihood these measurements will have the following characteristics. (1) They will not be administered at 3,6, 9 and 12 months. For some the schedule will lag. (2) Some children will miss one or more of these measurements.

Although some RCTs assume that measurements occur at the protocol-defined time, even when they do not, there is no reason for, and we shall deliberately avoid, that ad hoc practice.

We shall model the time of each measurement as the number of months (including factional amounts) from date of randomization. Time we shall model flexibly with splines. [Here we can use cubic splines as needed).

Choices for knots. We shall assume knots at time 3, 6 and 9 months, the intended dates of measurements.

With time measured flexibly, and with a statistical model that includes time by treatment (4 level) interactions, the spline model will allow for estimate of differences (or ratios) of outcomes at any point along the time (x) axis by treatment group.

Covariates -- selection and balancing

In theory randomization at the child level should balance on observed and unobserved factors. With children spread over 36 schools, and with chance differences across school, imbalances in child characteristics are possible at the school level but are not likely at the treatment assignment level (the four cells a, b, c and d). In addition, dropout can undermine the balance achieved in theory and in practice by randomization.

Key child-level covariates appear in Table 5.1.2.

Table 5.1.2 Covariates – baseline descriptions

Child level factors	Units of measurement or categories
AGE	Subgroups: 5-11; 12-13
GENDER	Male Female
Body mass index (weight in kg) (height in cm)	Collected and/or calculated by age-sex standardized percentile and/or z score. Both percentile and z will be used
HOUSEHOLD CHARACTERISTICS (descriptive only)	 (1) Single Parent/Caregiver vs Multiple Caregivers (2) Number of Adults in household (3) Number of Children in Household
Home environment	Number of bedrooms
Smoking	Smokers or none in home
Caregiver Education Highest level achieved by primary caregiver	Less than HS HS+ Graduate Level
Baseline Healthcare utilization	

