Oral Steroid courses in the last year	None 1 course 2 courses 3 5 courses
ED With include - But describe in categories	>5 courses
ED VISITS in the last year	0, 1, 2, 3+
Continuous – Describe in categories Inpatient visits in the last year Continuous—Describe in categories	0,1,2, 3+

Data on height and weight, and BMI, and BMIz, will be downloaded from EPIC. BMI categories of interest are <85th percentile, 85th to 95th percentile, and 95% percentile or greater. Height is not done at each encounter. For that reason, height must be carried forward from the last available measurement time. This practice, though common, can result in a bias toward higher than actual BMI over time. Adjustments (e.g., interpolation) of height for measurement times between height measures is possible. If any interpolation of height, we shall do so without regard to measures of outcome.

For that reason, we shall first examine balance across the 4 treatment groups in child-level characteristics. To that end, we shall use conventional balancing diagnostics, such as comparison of percentages of patients by categorical factors and by standardized differences for continuous

factors, and/or comparisons of distributions. All will be supplemented by graphical display. These diagnostics are programmed and explained in the R program "cobalt" (Greifer 2019).

Treatment assignment model

Covariates that do not demonstrate balance will be included in an initial multinomial logit model (with the 4 treatments as outcomes). Then using generalized propensity scores, we will develop inverse probability of treatment assignment weights. This approach will then result in estimates of average treatment effects in the response model.

Response model—to estimate expected values over time

The response model will be a weighted longitudinal model using splines for time and time by treatment interaction terms. This model will result in the estimation of expected values at any given time post randomization for any of the four treatment categories.

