5.1.2 Patient-level analysis – mixed effects models

First, linear mixed effects models with random intercepts and slopes for school, and fixed effects for the school-level intervention, time, and time-by-intervention interaction (the estimate of interest) will be applied. Likewise, the main effect for the child-level intervention and a time*intervention interaction term will be included in the model, and variation across multiple measurements on a child within a school will be accounted for by child-level random effects. This approach then becomes a three-level model with explicitly modeled random effects at the school and child levels.

Synergy of the effect of the two interventions will be estimated by the 3-way interaction between time, the school-level intervention, and the child-level intervention along with all corresponding two-way interactions.

Models will use numerical quadrature with least 12 quadrature points. Models with 16 quadrature points will be used to check sensitivity of results to numerical integration.

This and other individual-patient-level methods can be more efficient (smaller confidence bounds) than cluster (school)-level models. (Hayes and Moulton, section 11.4.2)

We shall exploit mixed effects models to estimate the degree of variation of effects across the 36 schools, both the 18 intervention schools and the 18 control schools by estimating the random slope component of variance and asking whether the observed variation across schools is greater than that expected at random.

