6.1.2.2 Estimating effect modification – scale dependency of interactions

Models for outcomes might be both additive (for asthma control) and multiplicative, as for use of log link generalized linear models. The contrasts of interest for permutation-test-based methods might also be additive (differences across the four treatment groups of differences in expected values over time).

Interaction (and effect modification) are scale dependent. A multiplicative model (log link) that has no interaction can give use to results that show effect modification on the additive scale. For that reason, we define "effect modification" to be on the additive scale for the key endpoints of change in asthma control scores and number of days of symptoms.

Estimation will follow the same principles and procedures as for the main analysis. Longitudinal data analysis models with splines for time will allow for estimation of expected values at time of randomization and at any time post randomization. For a single subgroup, the effect of the intervention (4 levels) can be compared by estimating eight expected values: four at time 0 and four at the endpoint time of interest. Contrasts across levels of the intervention and over time are estimated by subtraction.

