9.2 Statistical power

It is very likely that all attempts to demonstrate heterogeneity of treatment effect and/or mediation will fail owing to inadequate numbers of patients spread over a large number of schools.

10. Update to Data Analysis Plan: Impact of Pandemic Restrictions. Presented to and approved by Data Safety Monitoring Board (DSMB) on 6/29/2021:

The original statistical analysis plan (SAP) includes the fitting of longitudinal models to evaluate the impact of study interventions on primary and secondary outcomes in models that model time as months from randomization, with splines (knots at 0, 3, 6, 9 and 12 months) and time by treatment interaction terms. Mixed-effects and population-averaged (GEE) models will be fitted.

The initial analyses will be conducted as planned. **Sensitivity analyses** will then be performed to evaluate the impact of pandemic restrictions (pre and post^{*}, where *Post = Time Period after March 14, 2020).

Longitudinal models for the main analyses will be modified to include an indicator variable for post COVID-19 phase* with time by post Covid-19 interaction and time by post COVID-19 by intervention interaction terms. In these models, post Covid-19 phase will be included as a time varying covariate within individuals.

Post pandemic restrictions by time by intervention interaction terms: If significant, the impact of an intervention at a particular time point (e.g., at 3 months post-randomization) depends on post pandemic status (relative to pre).

Post pandemic restrictions by time terms: If significant, the expected value of the outcome at a particular time point depends on post pandemic status (relative to pre).

Post pandemic restrictions indicator variable: If significant, the expected value of the outcome variables depends on post pandemic status (relative to pre).

References:

Berger VW. Pros and cons of permutation tests in clinical trials. Stat Med. 2000; 19(10):1319-28. [PMID: 10814980]

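### The planned mixed model leaves A+ and A- baseline ACQ means free; if baseline preceded allocation, a common baseline would narrow child-level intervals by about 5 to 16% (correlation assumed)

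*SAP*

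**What the plan says.** A+ and A- are the SAP's labels for children with and without the primary care community health worker (P+ and P- in the protocol). Cells a and b are the A+ and A- children in intervention schools; c and d are those in control schools.

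- **Model.** SAP 5.1.2 (mixed effects models) says "the main effect for the child-level intervention and a time*intervention interaction term will be included in the model" and names the time-by-intervention term as the quantity to estimate. For synergy it adds the three-way term and all its two-way terms, which include A-by-S at time 0.
- **Endpoint.** Protocol 6.3.2: "The primary efficacy endpoint will be the change in asthma control between Study Visit 1 and Study Visit 5". SAP 6.1.2.2, which follows the main analysis, works by "estimating eight expected values: four at time 0 and four at the endpoint time of interest" and then subtracting.
- **Child allocation.** SAP 3.2: "Randomization was stratified by school and by clinic within school", in blocks of 2 and 4.
- **Other descriptions of the model.** SAP 5.1.2 (irregular measurement times): "The response model will be a weighted longitudinal model using splines for time and time by treatment interaction terms". SAP 10 describes the models as fitted "with splines (knots at 0, 3, 6, 9 and 12 months) and time by treatment interaction terms". Neither lists a treatment main effect. The knots differ too: the earlier section says "We shall assume knots at time 3, 6 and 9 months, the intended dates of measurements".
- **Baseline ACQ as a covariate.** No section names it. Table 5.1.2 omits it. SAP 5.3 could admit it only as an unnamed predictor of dropout. Baseline asthma control otherwise appears as a moderator (Protocol 6.3.3, SAP Table 6.1b).
- **Order of baseline and allocation.** Protocol 3.1.2, for the primary care arm: "Once consented and randomized, the CHW will collect baseline data". SAP 3.4 requires only signed consent before REDCap releases the assignment. Protocol 6.3.2 places randomisation at Study Visit 1, which is also the baseline visit.

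**The concern.** Children are randomised within school. If baseline ACQ is measured before anyone knows the allocation, the expected baselines of a and b are equal, and so are those of c and d. A model that still estimates a separate baseline mean for each arm, and subtracts it, carries the full sampling error of the baseline difference into the effect estimate. Using the known equality removes part of that error and needs no more children.

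What is at stake is interval width, not validity. It matters most for the single-cell comparisons of Aims 1b and 1c (a vs b, c vs d), because SAP 8 now projects about 100 children per cell where 150 had been expected. SAP 9 describes estimation as the overall goal, so precision counts whatever the significance tests show.

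**Working it through.** **1. The plan's own figures.** SAP 8 gives power for A+ vs A- at an effect of 0.35 SD of change with no interaction: 0.95 at n=432 and 0.99 at n=600. Treat the contrast as a two-sample comparison of change with SD 1, two-sided alpha 0.05 and no design effect, since it is made within school:

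- 216 per arm: 0.35/sqrt(2/216) - 1.96 = 1.68, power 0.953.
- 300 per arm: 0.35/sqrt(2/300) - 1.96 = 2.33, power 0.990.

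Both agree. A single-cell contrast at 108 per cell gives 0.730, against the simulated 0.71 (c vs d) and 0.75 (a vs b). The planning figures therefore behave like a plain comparison of change scores.

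**2. Variance with free and common baseline.** Let s² be the ACQ variance at each visit and rho the correlation between baseline and month 12. Per child:

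- free baseline (difference in change): 2s²(1 - rho)
- common baseline, or baseline as covariate: s²(1 - rho²)
- ratio: (1 + rho)/2, so the interval width is multiplied by sqrt((1 + rho)/2)

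**3. Interval width.** SAP 5.5 equates 0.5 SD of change with 0.4 ACQ points, so the SD of change is 0.4/0.5 = 0.8. The planned half-width at 108 per cell is 1.96 × 0.8 × sqrt(2/108) = 0.213 ACQ points. The documents give no rho; 0.4 to 0.8 is assumed.

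| rho | variance ratio | interval narrower by | half-width, c vs d or a vs b |
|---|---|---|---|
| 0.4 | 0.70 | 16.3% | 0.179 |
| 0.5 | 0.75 | 13.4% | 0.185 |
| 0.6 | 0.80 | 10.6% | 0.191 |
| 0.7 | 0.85 | 7.8% | 0.197 |
| 0.8 | 0.90 | 5.1% | 0.202 |

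**4. Does this survive the longitudinal model?** Generalised least squares on visits at 0, 3, 6, 9 and 12 months was run with saturated, linear-spline, natural cubic spline and straight-line time. Each was combined with compound-symmetry, autoregressive and random intercept-and-slope covariance. The narrowing was about 4 to 17% with complete data and about 3 to 16% with an assumed 30% dropout. The starting width can differ. With straight-line time or a three-knot natural cubic spline under compound symmetry, the planned model already has 0.80 of the change-score variance, so it starts at 0.213 × sqrt(0.80) = 0.191.

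**5. What if baseline was taken with allocation known?** Suppose this knowledge shifts the A+ baseline report by d.

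| shift | change contrast off by | adjusted contrast off by |
|---|---|---|
| at baseline only | d | about rho × d |
| persists to follow-up | 0 | about (1 - rho) × d |

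With d = 0.2 and rho = 0.4, 0.6, 0.8, the sizes are 0.20 against 0.08, 0.12, 0.16 in the first case, and 0 against 0.12, 0.08, 0.04 in the second. A simulation of 18 schools with 12 children each agreed. Neither model is safe in both cases.

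**The case against.** **Timing.** A reader might take this for a free gain. The documents do not support that. The only explicit ordering, in Protocol 3.1.2, puts baseline after randomisation, and for A+ children the worker who delivers the intervention collects it. SAP 3.4 does not contradict this, because consent is all it requires first. If a reporting shift persisted, the planned contrast would be unbiased and the adjusted one would not. This objection stands and makes the recommendation conditional.

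**The plan may already do it.** Read literally, with spline terms that are zero at time 0, the response model in SAP 5.1.2 and the description in SAP 10 have no treatment difference at baseline. They may be shorthand. The mixed-model section and SAP 6.1.2.2 point the other way. The matter is unsettled, which is itself a reason to write the terms down.

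**A different estimand.** SAP 5.1.2 also allows group differences at any time point. For a month-12 difference from a free-baseline model with saturated time, the gain would be 1 - sqrt(1 - rho²), or 8 to 40%. The larger figure is not claimed, because the stated estimate of interest is time-by-intervention and the protocol endpoint is change.

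**Power.** A reader might infer that the 0.71 and 0.75 are the model's fault and would be repaired. They fall from 0.85 and 0.87 because the sample is smaller, and SAP 8 keeps them as a historical record. No power gain is claimed here.

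**Reach.** The ratio ignores the treatment-assignment weights in SAP 5.1.2 and does not cover the possible log-gamma model in SAP 5.1.3, which estimates a ratio and not a difference. The permutation analysis in SAP 5.1.4 is headed as school-level and is outside this point.

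**Conclusion.** The planned child-level contrast is valid, and nothing here shows bias in it. It gives up precision. With rho of 0.4 to 0.8, 12-month intervals for A+ vs A-, a vs b and c vs d would be about 5 to 16% narrower with a common baseline (about 4 to 17% across the time and covariance models tried with complete data). In variance terms, this equals 1/0.90 to 1/0.70, or about 11 to 43% more children for those contrasts.

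The conclusion rests on an assumed correlation, on an SD of change of 0.8 implied by SAP 5.5, on an identity-scale analysis, and above all on baseline ACQ having been recorded before allocation was disclosed. The documents do not establish that last condition, and Protocol 3.1.2 suggests otherwise. School contrasts were not assessed. This is an improvement to consider, not a defect that threatens the result.

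**What to change.** Make a dated SAP amendment before outcomes are examined. The SAP was finalised on 13 September 2022, and under SAP 9.1 analyses added after it without prespecification are exploratory.

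1. From REDCap time stamps, and without outcome data, tabulate how many children had baseline ACQ recorded before the allocation was disclosed.
2. If baseline came first, estimate child-level contrasts in the mixed model with one A+/A- mean at time 0: drop the A and A-by-S terms at time 0, keep their interactions with time, and keep the S term. In the identity-link GEE, use follow-up visits as outcomes with baseline ACQ as a covariate.
3. If a material share of baselines followed disclosure, keep the planned change contrast and report the baseline-adjusted estimate beside it.
4. Whatever the timing, state which treatment terms exist at time 0, so that the response model and mixed-model parts of SAP 5.1.2 agree with SAP 10.

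The cost is SAP wording and one time-stamp check; no new data are needed. The downside is the persistent-shift case, where the adjusted estimate is off by about (1 - rho) × d, so step 1 must come before step 2.
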